## 2.3 Benefit/Risk Assessment

The benefit/risk assessment of KOVALTRY has been demonstrated as favorable in the LEOPOLD program for children, adolescents, and adults.

In general, in clinical trials of both children and adolescents/adults, KOVALTRY has been shown to be well tolerated.

The most significant risk with KOVALTRY, like any FVIII replacement product, is the development of FVIII inhibitors. Detailed information about the known and expected benefits and risks and expected adverse events of KOVALTRY may be found in the Chinese Package Insert (see Section 12).

### 2.3.1 Risk Assessment

Potential Risk of Clinical Significance	Summary of Data/ Rationale for Risk	Mitigation Strategy
Important identified risks: 
 
Development of factor VIII inhibitors
 
Hypersensitivity and allergic reactions
 
	
Development of factor VIII inhibitors: The formation of neutralizing antibodies (inhibitors) to FVIII is a known complication in the management of individuals with hemophilia A and a class effect for all FVIII products. For previously untreated patients (PUPs), the risk to develop inhibitors is considered very common (approximately 30% to 50%), whereas the risk for PTPs is considered uncommon (<1%).
 
Hypersensitivity and allergic reactions: Hypersensitivity reactions, including anaphylaxis, are possible with KOVALTRY. No anaphylactic reactions have been reported with KOVALTRY. Allergic type hypersensitivity reactions are possible with KOVALTRY. The product may contain traces of hamster or mouse proteins, which in some patients may cause allergic reactions.
	
The informed consent will outline the important identified and potential risks.
 
Inhibitor titer is assessed at scheduled study visits.
 
Planned time points for all safety assessments are provided in the Schedule of Activities [Section 1.3].

Study Intervention - KOVALTRY		
Drug infusion: This procedure can cause pain or bruising at the site of the infusion.	The study treatment is administered as intravenous infusion [see Section 6.1].	Study participants will be informed of these potential risks in the informed consent.
Study Procedures		
Blood draw: This procedure can cause discomfort from the needle, pain, and bruising at the site of the draw.  There is rarely any infection. Drug infusion: This procedure can cause pain or bruising at the site of the infusion.	Blood samples will be obtained at baseline to confirm study eligibility. As outlined in Section 7.1 and Section 7.2, there will be additional blood draws at scheduled study visits for FVIII recovery, FVIII inhibitor assessment, and for a subset of participants in Part A, additional PK analysis sampling.	Study participants will be informed of these potential risks in the informed consent.

### 2.3.2 Benefit Assessment

Hemophilia A is an X-linked, congenital, potentially life-threatening disease that is caused by a deficiency of FVIII and results in impaired blood clotting. Patients with hemophilia A require infusions of replacement FVIII to prevent and treat spontaneous and trauma-related bleeding episodes. KOVALTRY is a full-length rFVIII product approved for the prevention and treatment of bleeding episodes in patients with hemophilia A. The LEOPOLD clinical trial program conclusively demonstrated that KOVALTRY is efficacious in preventing and treating bleeding episodes as well as maintaining hemostasis during surgery in children, adolescents, and adults with severe hemophilia A.

Prophylaxis with KOVALTRY decreases bleeding frequency compared with on-demand treatment. KOVALTRY prophylaxis is efficacious when administered either twice weekly or three times weekly, and in addition in pediatric patients also every other day. LEOPOLD study data support the use of individualized prophylaxis dosing of KOVALTRY based on a patient's clinical history. In the LEOPOLD clinical studies, a low pre-study bleeding rate was a good predictor of a low annualized bleeding rate with KOVALTRY prophylaxis. KOVALTRY also effectively maintains hemostasis in patients with hemophilia A undergoing major or minor surgical procedures.

The risk associated with infusion of study treatment is not more than what would be expected for hemophilia A patients receiving KOVALTRY as standard of care.

Blood samples will be collected at screening to confirm study eligibility, during scheduled study visits as part of safety assessment for the study, and for the PK sub-study (optional for children <12 years of age) in Part A. The frequency of these assessments is likely more than is typical for standard of care. The study has kept the frequency of these assessments to the minimum required to reliably assess the safety of KOVALTRY in study participants. For the majority of participants in the study, the volumes drawn at any one visit are not expected to exceed more than 1% of total blood volume or 3% in any 1-month interval. Additionally, the protocol includes a guideline providing the recommended blood volume to be drawn from children 1-10 kg for study related tests. Therefore, it is expected that the risk associated with blood draws is not more than would be expected with standard of care.

### 2.3.3 Overall Benefit: Risk Conclusion

Considering the measures taken to minimize risk to participants in this study, the potential risks identified in association with KOVALTRY are justified by the anticipated benefits of prophylaxis treatment with KOVALTRY for study participants.

### 3. Objectives and Endpoints

#### 3.1 Objectives and Endpoints - Part A (PTPs)

Objectives	Endpoints
Primary Efficacy	

 
Evaluate the efficacy of prophylaxis treatment with KOVALTRY in Chinese children (<12 years) and adolescents/adults (<math>\geq 12</math> years) with severe hemophilia A
 
	
 
Annualized bleeding rate (ABR)
 

Secondary Efficacy	

 
Evaluate efficacy of KOVALTRY for treatment of bleeding episodes
 
Assess efficacy within 48 hours of previous prophylaxis infusion
 
Evaluate the in vivo recovery of KOVALTRY
 
Hemostatic control for minor surgeries
 
	
 
Number of infusions needed to achieve hemostasis and response to treatment of bleeds
 
ABR within 48h of previous prophylaxis infusion
 
In vivo recovery of KOVALTRY at baseline, 2 months after start of study treatment, and study end
 
Physician assessment of adequacy of hemostasis in minor surgery
 

Safety	

 
Assess the safety of KOVALTRY for prophylaxis and treatment of bleeding episodes in Chinese children (<12 years) and adolescents/adults (<math>\geq 12</math> years) with severe hemophilia A
 
	
 
FVIII inhibitor development by the Nijmegen Bethesda assay
 
Treatment-emergent adverse events (TEAEs)
 

Pharmacokinetics	

 
Evaluate pharmacokinetics (PK) of KOVALTRY in Chinese children (<12 years) and adolescents/adults (<math>\geq 12</math> years to 65 years) severe hemophilia A patients
 
	
 
PK parameters include <math>C_{max}</math>, AUC, and <math>t_{1/2}</math>
 

### 3.2 Objectives and Endpoints - Part B (PUPs/MTPs)

Objectives	Endpoints
Primary Efficacy	

 
Assess the efficacy of KOVALTRY within 48 hours of previous prophylaxis infusion in previously untreated/minimally treated Chinese children (<6 years of age) with severe hemophilia A
 
	
 
ABR within 48 hours of previous prophylaxis infusion
 

Secondary Efficacy	

 
Evaluate the efficacy of prophylaxis treatment with KOVALTRY
 
Assess the efficacy of KOVALTRY for treatment of bleeding episodes
 
Evaluate the in vivo recovery of KOVALTRY
 
Hemostatic control for minor surgeries
 
	
 
ABR during the prophylaxis period
 
Number of infusions required to treat a bleed and response to treatment of bleeds
 
In vivo recovery of KOVALTRY at baseline and study end
 
Physician assessment of adequacy of hemostasis in minor surgery
 

Safety	

 
Assess the safety of KOVALTRY for prophylaxis and treatment of bleeding episodes in previously untreated/minimally treated Chinese children (<6 years of age) with severe hemophilia A
 
	
 
FVIII inhibitor development by the Nijmegen Bethesda assay
 
Treatment-emergent adverse events (TEAEs)
 

## 4. Study Design

### 4.1 Overall Design

This is a multicenter, uncontrolled, open-label, single arm treatment, 2-part study in previously treated, previously untreated, and minimally treated Chinese children and adolescents/adults with severe hemophilia A.

Study participants who develop high-titer inhibitor (>5 BU/mL, confirmed by central lab for Part A or local laboratory for part B) related to study drug, that interferes with effective treatment with FVIII, may opt to enter optional ITI treatment with study drug (Section 10.5.1) or leave the study and be treated with other therapies outside of the study at the discretion of the investigator. The optional ITI treatment with the study drug within the study requires a separate signed informed consent. Refer to Section 10.5 for additional details.

#### 4.1.1 Part A (PTPs)

Part A will assess the efficacy, safety, and PK of KOVALTRY in previously treated Chinese children and adolescents/adults with severe hemophilia A. Part A is planned to investigate a total of 42 PTPs. Efficacy and safety assessments are outlined in the Schedule of Activities (SoA) in Section 1.3.1.

PK will be assessed in a subset of 12 children (<12 years) and 12 adolescents/adults (≥12 years). Details of the PK parameters to be assessed are provided in Section 8.6.

Efficacy and safety data for use of KOVALTRY for treatment of bleeding episodes will also be collected.

- Study participants will be treated for 6 months at the following doses according to the prescribing information for KOVALTRY:
  - Study participants ≤12 years of age: 25 to 50 IU of KOVALTRY per kg body weight twice weekly, three times weekly, or every other day according to individual requirements for 6 months
  - Study participants >12 years: 20 to 40 IU of KOVALTRY per kg of body weight two or three times per week according to individual requirements for 6 months
- Part A will include 5 study visits (Screening, Baseline, Visit 3/Month 1, Visit 4/Month 2, Visit 5/Final visit/Early Termination). All participants will also receive a safety follow-up call approximately 2 weeks after the final study visit.

#### 4.1.2 Part B (PUPs/MTPs)

Part B will assess the efficacy and safety of KOVALTRY in previously untreated/minimally treated Chinese children with severe hemophilia A. Part B will investigate approximately 6 PUPs/MTPs. Efficacy and safety assessments are outlined in the SoA in Section 1.3.2.

Efficacy and safety data for the use of KOVALTRY for treatment of bleeding episodes will also be collected.

- Study participants will be treated until at least 50 ED is achieved.
  - Treatment may begin with start of prophylaxis with 15 to 50 IU/kg (minimum dose: 250 IU) at least 1 day a week; alternatively, prophylaxis

can be started directly with a once-a-week schedule minimum dose of 250 IU for PUPs/MTPs of any weight.

- The starting dose may be tailored to the participant's weight or demonstrated bleeding tendency.
- Individual participant dose decisions are at the discretion of the investigator.
- Part B will include 8 study visits (Screening, Baseline, Visit 3 [approximately 5 ED], Visit 4 [approximately 10 ED], Visit 5 [approximately 15 ED], Visit 6 [approximately 20 ED], Visit 7/Interim visit [approximately 30 to 40 ED], and Visit 8/Final visit [50 ED]/Early Termination). All parents/caregivers of participants in Part B will receive a safety follow-up call approximately 2 weeks after the end of treatment.

## 4.2 Scientific Rationale for Study Design

Part A of this study will collect clinical data in 42 previously treated Chinese participants with severe hemophilia A (30 children and 12 adolescents/adults) to provide additional efficacy and safety data for the use of KOVALTRY for prophylaxis and treatment of bleeding episodes in this patient population. Pharmacokinetic data will also be collected from 24 participants (see Section 8.6 for details).

Part B of this study will collect clinical data in approximately 6 previously untreated/minimally treated Chinese participants with severe hemophilia A (6 children) to provide additional efficacy and safety data for the use of KOVALTRY for prophylaxis and treatment of bleeding episodes in this patient population.

### 4.2.1 Participant Input into Design

Not applicable.

## 4.3 Justification for Dose

The routine prophylaxis doses used in this study are the approved doses in the Chinese prescribing information for KOVALTRY (Section 12).

### 4.3.1 Routine Prophylaxis

- Adults and adolescents: 20 to 40 IU of KOVALTRY per kg of body weight two or three times per week
- Children  $\leq$ 12 years old: 25 to 50 IU of KOVALTRY per kg body weight twice weekly, three times weekly, or every other day according to individual requirements

Prophylactic treatment regimens should be guided by clinical judgement based on individual patient characteristics and treatment response.

#### 4.3.1.1 Prophylaxis Treatment for Adolescent and Adult Patients

For long-term prophylaxis against bleeding in patients with severe hemophilia A, the recommended doses are 20 to 40 IU of factor VIII per kg body weight two or three times per week. In some cases, especially in younger patients, shorter dosage intervals or higher doses may be used.

#### 4.3.1.2 Pediatric Patients

KOVALTRY is approved for use in pediatric patients. Safety and efficacy studies have been performed in children 0-12 years. The recommended prophylaxis doses are 25-50 IU/kg twice weekly, three times weekly, or every other day according to individual requirements. For pediatric patients above the age of 12, the dose recommendations are the same as for adults.

For PUPs/MTPs, prophylaxis with study intervention may be initiated at 15 to 50 IU/kg (minimum dose: 250 IU) at least 1 day per week.

Frequent infusions may be difficult for small children and their caregivers. Consequently, the benefit for each individual child must be evaluated against this burden, particularly in very young children for whom venous access may be difficult.

#### 4.3.2 Treatment of Bleeding Episodes

The required dose is determined using the following formula:

$$\text{Required units} = \text{body weight (kg)} \times \text{desired factor VIII rise (\% or IU/dL)} \times \text{reciprocal of observed recovery}$$

The usual single dose for bleeding episodes of mild to moderate severity is 10-30 IU/kg body weight. Higher dosages are recommended for life threatening or major hemorrhages.

For participants with a recovery below 2 (which may occur, e.g., in small children), higher dosages may be needed. Further guidance is included in Section 12.

#### 4.4 End of Study Definition

A participant is considered to have completed the study if he has completed the last study visit, as shown in the Schedule of Activities for Part A (Section 1.3.1) or Part B (Section 1.3.2), or optional ITI treatment (Section 10.5.2).

Completion of Part A is when the last participant in Part A completes the final visit or early termination as shown in the Schedule of Activities for Part A (Section 1.3.1).

Completion of Part B is when the last participant in Part B completes the final visit or early termination as shown in the Schedule of Activities for Part B (Section 1.3.2).

Study participants who develop high-titer FVIII inhibitor and decide to enter optional ITI treatment with study intervention will discontinue participation in either Part A or Part B and complete the Early Termination visit. The end of study for these participants is defined as completion of the Optional ITI Treatment (Section 10.5.1).

Study participants who develop high titer FVIII inhibitor and decide to receive ITI with another product outside of the study will complete the Early Termination visit and leave the study.

The study itself will be considered complete after the last visit of the last participant for all centers has occurred.

## 5. Study Population

Part A of the study plans to enroll 42 previously treated severe hemophilia A, defined as less than 1% of factor VIII in the blood (based on one-stage assay), patients (PTPs) in China.

Approximately 30 children aged <12 years and 12 adolescents/adults  $\geq$ 12 years up to 65 years with documented severe hemophilia A will be enrolled in two age groups.

Part B of the study plans to enroll approximately 6 Chinese PUPs/MTPs (children <6 years) with documented severe hemophilia A, defined as less than 1% of factor VIII in the blood (based on one-stage assay).

Prospective approval of protocol deviations to recruitment and enrollment criteria, also known as protocol waivers or exemptions, is not permitted.

### 5.1 Inclusion Criteria

#### 5.1.1 Part A (PTPs) Inclusion Criteria

Participants are eligible to be included in Part A of the study only if all of the following criteria apply:

##### Age

1. Participants enrolled as children must be <12 years at the time of their parent or legal representative's signature of informed consent on the participant's behalf, or if enrolled as adolescents/adults, must be  $\geq$  age 12 to 65 years at the time of signed informed consent.

##### Type of Participant and Disease Characteristics

2. Chinese participants with severe hemophilia A (defined as FVIII:C <1% with one-stage clotting assay documented at the time of screening). If screening results show FVIII:C as equal to or higher than 1%, then severe hemophilia A may be confirmed by documented historical evidence from a (certified) clinical laboratory demonstrating <1% FVIII:C as determined by a one-stage clotting assay.
3. Currently receiving on-demand or any type of prophylaxis treatment regimen with any FVIII product (excluding treatment with fresh-frozen plasma and cryo-precipitate).
4. For participants <12 years of age,  $\geq$ 50 exposure days (ED); for participants  $\geq$ 12 to 65 years of age,  $\geq$ 150 ED with any Factor VIII product (excluding treatment with fresh-frozen plasma and cryo-precipitate).
5. No current evidence of inhibitor antibody as measured by the Nijmegen-modified Bethesda assay [ $<0.6$  Bethesda units (BU)/mL] in 2 consecutive samples and absence of clinical signs or symptoms of decreased response to FVIII administration. (First negative sample can be historical if obtained within 3 months prior to screening with a result of  $<0.6$  BU/mL by classical Bethesda assay. The testing for a second negative, confirmatory sample must, in all cases, be performed by a central laboratory using the Nijmegen-modified Bethesda test. If a first recent sample is not available, then testing for 2 negative samples must be performed by the central laboratory at least 1 week apart). Participants may not receive FVIII within 72 hours prior to the collection of samples for inhibitor testing.

6. No history of FVIII inhibitor formation. Documentation of negative result in medical records is required (Nijmegen-modified Bethesda assay or classical Bethesda assay); participants with a maximum historical titer of 1.0 BU/mL on no more than 1 occasion with the classical Bethesda assay but at least 3 successive negative results (<0.6 BU/mL) thereafter are eligible.

**Sex**

7. Male participants only.

**Informed Consent**

8. Each adult participant must be capable of giving signed informed consent/assent as described in Section 10.1.2, which includes compliance with the requirements and restrictions listed in the informed consent form (ICF) and in this protocol. For children and adolescents under the age of consent/assent in China, parents or a legal representative must be able to provide a signed informed consent/assent on behalf of the minor child/adolescent.

**Other**

9. Willingness and ability of participants, parents, or caregiver to comply with prophylaxis schedule and complete training on the use of the study electronic patient diary (EPD) and to use the diary to document bleeding and infusion information during the study.

**5.1.2 Part B (PUPs/MTPs) Inclusion Criteria**

Participants are eligible to be included in Part B of the study only if all of the following criteria apply:

**Age**

1. Participants must be <6 years of age at the time of their parent or legal representative's signature of informed consent on the participant's behalf.

**Type of Participant and Disease Characteristics**

2. Chinese participants with severe hemophilia A (defined as FVIII:C <1% with one-stage clotting assay documented at the time of screening). If screening results show FVIII:C as equal to or higher than 1%, then severe hemophilia A may be confirmed by documented historical evidence from a (certified) clinical laboratory demonstrating FVIII:C <1% as determined by a one-stage clotting assay.
3. PUPs must have no previous exposure to any FVIII product.  
MTPs must have no more than 1 ED with any purified FVIII concentrate or 3 exposures with FFP or cryoprecipitate.
4. MTPs have no current evidence of inhibitor antibody as measured by the Nijmegen-modified Bethesda assay (<0.6 BU/mL) in 2 consecutive samples and must have absence of clinical signs or symptoms of decreased response to FVIII administration. Testing for the 2 negative samples must be performed by the local laboratory at least 1 week but not more than 2 weeks apart. Participants may not receive FVIII product within 72 hours prior to the collection of samples for inhibitor testing.

5. PUPs and MTPs must observe a 6-month washout period if they have received subcutaneous factor substitution therapy (emicizumab).
6. PUPs may be included if they will receive their first FVIII dose with KOVALTRY for treatment of first bleeds and agree to start prophylaxis as part of their care.  
MTPs may be included if they agree to start prophylaxis as part of their care.

**Sex**

7. Male participants only

**Informed Consent**

8. The parents or a legal representative of the participant must be able to provide a signed informed consent on behalf of the participant.

**Other**

9. The participant's parent/caregiver must be willing and able to comply with the prophylaxis schedule and to complete training on the use of the study EPD and use the EPD to document bleeding and treatment information during the study.

**5.2 Exclusion Criteria****5.2.1 Part A (PTPs) Exclusion Criteria**

Participants are excluded from Part A of the study if any of the following criteria apply:

**Medical Conditions**

1. Any other bleeding disease that is different from hemophilia A (e.g., von Willebrand disease, hemophilia B).
2. Platelet count <100 000/mm^3 based on screening laboratory assessments.
3. Impaired renal function (serum creatinine >2.0 mg/dL) or active liver disease (alanine aminotransferase/aspartate aminotransferase [ALT/AST] >5x ULN) based on screening laboratory.
4. Human immunodeficiency virus (HIV) positive with an absolute CD4 lymphocyte cell count <250 cells/µL.
5. Known hypersensitivity to the active substance, mouse or hamster protein.

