**Prior/Concomitant Therapy**

6. Receiving chemotherapy or immune modulatory drugs (e.g., intravenous [IV] immunoglobulin, cyclosporine) other than anti-retroviral chemotherapy or chronic use of oral or intravenous (IV) corticosteroids (>14 days) within the last 3 months. Brief courses of prednisone/methylprednisolone (<14 days) for treatment of disorders such as synovitis, asthma, etc. are allowed at the discretion of the treating physician
7. Requiring any pre-medication to tolerate FVIII infusions (e.g., antihistamines).

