**Other Exclusions**

9. Unwilling to comply with study visits or other protocol requirements or is not suitable for participation in this study for any reason, according to the Investigator.
10. Planned major surgery, defined as surgery with respiratory assistance and/or general anesthesia.
11. Close affiliation with the investigational site; e.g., a close relative of the investigator, dependent person (e.g., employee or student of the investigational site).

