**Other Exclusions**

11. Unwilling to comply with study visits or other protocol requirements or is not suitable for participation in this study for any reason, according to the investigator's judgment.
12. Close affiliation with the investigational site (e.g., a close relative of the investigator, dependent person [e.g., employee or student of the investigational site]).
13. Unable to tolerate volume of blood draws required for study participation (see Section 10.2).

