#### [Composition]

KOVALTRY is a sterile, stable, purified, non-pyrogenic dried concentrate produced by a genetically engineered Baby Hamster Kidney (BHK) cell line into which the human Factor VIII gene was introduced together with the human heat shock protein 70 (HSP 70) gene.

Active ingredient: Recombinant coagulation factor VIII.

Excipients: glycine, sucrose, sodium chloride, calcium chloride, histidine and polysorbate80.

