### **[Contraindications]**

KOVALTRY is contraindicated in patients who have a history of hypersensitivity reactions to the active substance, to any of the excipients, or to mouse or hamster proteins. (See [Composition])

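### Exclusion criterion 5 in both parts leaves out hypersensitivity to the excipients, which the attached label lists as a contraindication

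*Protocol*

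**What the plan says.** Criterion 5 under Medical Conditions has the same wording and number in protocol 5.2.1 (Part A) and 5.2.2 (Part B): "Known hypersensitivity to the active substance, mouse or hamster protein".

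The package insert in Section 12 gives the contraindication as a "history of hypersensitivity reactions to the active substance, to any of the excipients, or to mouse or hamster proteins". Its [Composition] entry lists them: "Excipients: glycine, sucrose, sodium chloride, calcium chloride, histidine and polysorbate80".

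Section 5 says of the enrollment criteria: "Prospective approval of protocol deviations to recruitment and enrollment criteria, also known as protocol waivers or exemptions, is not permitted". Sections 7.1.1 and 7.2.1 add that nobody should be dosed unless every inclusion and exclusion criterion is satisfied. The SAP does not deal with eligibility.

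**The concern.** The criterion looks like a transcription of the label contraindication with the middle item dropped. Read literally, it admits a patient whom the product's own label says should not receive it.

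A criterion written into Section 5 is checked at every site and cannot be waived. A contraindication that appears only in the attachment depends on someone recalling it and acting on it. A partial list carries a further risk, because a site may take it as the complete eligibility rule on hypersensitivity.

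The subject matters to this trial. Hypersensitivity is an important identified risk in 2.3.1 and one of the two adverse events of special interest in 8.4.7. Section 6.5 also forbids pre-medication to tolerate KOVALTRY, so a susceptible patient could not be managed that way once enrolled. What is at stake is the safety of a rare individual participant. The estimates are not at stake.

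**Working it through.** No formula applies and the plan states no figure to reproduce. The check is a comparison of texts, followed by a search for any other rule that closes the gap.

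**Step 1: criterion 5 against the label.**

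| Category in the label contraindication | Part A criterion 5 | Part B criterion 5 |
|---|---|---|
| Active substance | named | named |
| Any of the excipients | absent | absent |
| Mouse or hamster protein | named | named |

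Criterion 5 covers 2 of 3 categories in each part. The missing category comprises the six substances in the [Composition] list.

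**Step 2: the remaining exclusion criteria.** Part A has 11 and Part B has 13. The number that name excipients is 0 of 11 and 0 of 13. The inclusion criteria in 5.1.1 and 5.1.2 do not mention them either.

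**Step 3: criteria that might catch such a patient indirectly.**

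- *Pre-medication* (Part A criterion 7, Part B criterion 9): "Requiring any pre-medication to tolerate FVIII infusions (e.g., antihistamines"). This would exclude a patient whose excipient reaction shows itself as a need for pre-medication with FVIII. It misses an excipient allergy that needs none. It also has nothing to act on in a previously untreated patient, because Part B inclusion criterion 3 says "PUPs must have no previous exposure to any FVIII product".
- *General suitability* (Part A criterion 9, Part B criterion 11): a patient is excluded who "is not suitable for participation in this study for any reason, according to the Investigator" in Part A, or who "is not suitable for participation in this study for any reason, according to the investigator's judgment" in Part B. Either could exclude the patient, but only if the investigator decides so.

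**Step 4: safeguards outside the eligibility criteria.**

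- Section 2.3 refers investigators to the package insert for risk information. Section 6.1 ties the choice of regimen to the prescribing information, but it is not an eligibility rule.
- Part A gives the first dose in hospital (7.1.2). Part B does so for minimally treated patients and for previously untreated patients who start at Baseline (7.2.2). For previously untreated patients generally, 7.2.2 only recommends a first dose at the study center.
- In-hospital dosing helps manage a reaction. It does not prevent exposure of a contraindicated patient.

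No stated criterion excludes such a patient by name. Exclusion rests mainly on judgment, with partial help from the pre-medication criterion.

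**The case against.** The strongest reply is that the omission has almost no practical weight.

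- The risk table in 2.3.1 and the hypersensitivity paragraph under [Precautions] name only rodent proteins as a specific source, and criterion 5 covers these. The documents attribute no reaction to an excipient. The label's adverse-reaction table shows hypersensitivity in 1 of 193 previously treated patients (0.5%), and 2.3.1 reports no anaphylactic reaction with KOVALTRY.
- The excipients are common substances such as sodium chloride, glycine and sucrose, so counting six of them says little about risk.
- The suitability criteria are themselves stated criteria that cannot be waived. Once the investigator judges a patient unsuitable, exclusion is mandatory. To enroll a patient with a known excipient reaction, the investigator would have to act against a label bound into the protocol.
- Any amendment needs ethics committee approval (10.1.1), so the change is cheap only if it travels with others.

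Most of this stands as an argument about weight, and it is why the point ranks at the bottom of the scale. It does not remove the mismatch. The label's contraindication makes no exception for excipients, whichever source 2.3.1 chooses to name. The suitability criteria bind only after an individual judgment has been made, whereas a named exclusion requires none. The protocol chose to restate the contraindication in its criteria, and neither amendment summary gives a reason for a shorter list.

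**Conclusion.** The concern holds as a minor mismatch between criterion 5 and the protocol's own attachment, in both parts. One of the label's three hypersensitivity categories is missing, and no other criterion names it.

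Few or no participants are likely to be affected among the planned 42 in Part A and approximately 6 in Part B. That is a judgment. The documents give no prevalence of known excipient hypersensitivity, so no expected count is offered. The conclusion assumes that the attached insert is the label in force for the trial and that criterion 5 was meant to reflect its contraindication.

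**What to change.** Reword criterion 5 in 5.2.1 and 5.2.2 so that it excludes known hypersensitivity to the active substance, any excipient, or mouse or hamster protein, in line with the [Contraindications] entry in Section 12. No new screening item is needed, because 7.1.1 and 7.2.1 already require a complete medical history and verification of eligibility.

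The cost is one phrase in two criteria and at most a rare extra screen failure. Because ethics approval is required for any amendment, the change should go into the next amendment made for other reasons. The SAP needs no change.
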